7.5 Interim Analyses and Data Monitoring (as applicable)

(ICH E3; 9.7.1, 11.4.2.3. ICH E9; 4.1, FDA Feb 2010 "Guidance for Industry Adaptive Design Clinical Trials for Drugs and Biologics")

7.5.1 Purpose of Interim Analyses

The interim analyses were performed due to uncertainty about some aspect or aspects of the treatment or treatments and the interim will allow learning to influence the subsequent design of the study. This included the simple uncertainty about safety aspects and the primary endpoint treatment effect that leads to early termination for futility of efficacy.

7.5.2 Planned Schedule of Interim Analyses

An interim analysis was performed after half of the participant's 6-month follow-up visits were completed.

7.5.3 Scope of Adaptations and Stopping Rules

If the effect size of the intervention vs control exceeded 3.0 with a 95% CI of 2.5 to 3.5, then the intervention was to be deemed to be effective and study was to stop. As well, study participants who had not yet completed the intervention, i.e., were in physical therapy, and were in the control condition would have been offered the intervention. As well, we tallied the number of AEs, and compared that number between the intervention and control groups. If the intervention group was found to have more than three times the odds of AEs with a 95% CI of 2.5 to 3.5 compared with the control, then the study was to be stopped. Neither of

these events (efficacy or excessive AEs) occurred in the interim analyses.

7.5.4 Practical Measures to Minimize Bias

The interim analysis was performed by a single research assistant. This research assistant was the only person to see the data. She presented the results to the study's principal investigator to make decisions. This analyses was not made publicly available.

The final analyses will be performed by a statistician who will be blinded to group assignment. In particular, the study's principal investigator will draft mock tables for the statistician to fill out with data. Note the groups will be described as group 1 and group 2. Only after the tables are completely filled out, will the study's principal investigator become unblinded to determine which group (intervention vs control) is assigned to group 1 and group 2, and edit the tables accordingly.

8 Summary of Study Data

All continuous variables will be summarized using the following descriptive statistics: n (non-missing sample size), mean, and standard deviation. The frequency and percentages (based on the non-missing sample size) of observed levels will be reported for all categorical measures. In general, all data will be listed, sorted by treatment and subject, and when appropriate by visit number within subject. All summary tables will be structured with a column for each treatment in the order (Control, Experimental) and will be annotated with the total population size relevant to that table/treatment, including any missing observations.

8.1 Subject Disposition

We establish how many subjects reached the various stages of the trial (Enrollment, Allocation, Follow-up, and Analysis) using the following list:

Enrollment:

Declined to be contact by research Age < 45 Previous or planned surgery Comorbidity that precludes physical activity Already participated in a Delaware ACTIVE Lab study Did not receive a TKR Not interested Unable to contact Dropped out prior to randomization

Allocation:

Did not receive allocated intervention

Follow-up:

Lost to Follow-up Discontinued the intervention

CONSORT Diagram Template

8.2 Demographic and Baseline Variables

Characteristic [mean ± SD or n (%)]	All n=	Intervention n=	Control n =
Age (years)			
Gender (female)			
BMI (kg/m²)			
Race (Non-White)			

Comorbidity (Health History Questionnaire)		
MVPA at baseline (minutes/day)		
Steps/day at baseline		
Days between TKR and PT Evaluation		

8.3 Treatment Compliance

Characteristic [mean ± SD or n (%)]	All n=	Intervention n =	Control n =
Days Randomization to Discharge			
Days Eval to Discharge			

Characteristic [mean ± SD or n (%)]	Intervention n =
Percent of days in PT in the study that the Fitbit was checked (recorded or checked on HEP):	
Percent of weeks in PT in the study that a step goal was recorded:	

9 Efficacy Analyses

The primary and secondary outcomes will be summarized stratified by treatment group at each study timepoint (baseline, discharge, 6-month, 12-month). Our primary analysis will use an intention-to-treat (ITT) analysis that includes all participants who wore the monitor for \geq 4 days at baseline. The statistical model underlying the analysis a mixed-effects model to examine the main and interaction effects of *group* (Intervention vs. Control) and *time* (BL, DC, 6M, and 12M) on MVPA (minutes/day). We will adjust this model for age, sex, and body mass index. The null hypothesis is that there is no difference in change in MVPA in the intervention group compared to the control group. The alternative hypothesis is that there is a difference between groups. The nature of the hypothesis is confirmatory as this study has been powered to detect a difference should one exist. The mixed-effect model will be used to calculate the mean and 95% Confidence Interval time in MVPA at each study time point. We will also calculate difference in means and 95% Confidence Intervals between the intervention and control group at each study time point. We will also calculate 2-sided p-values to determine statistical significance of differences between groups by time in MVPA.

• Methods and assumptions for handling longitudinal data or missing data.

Mixed-effect modeling will be used to estimate MVPA over time. The mixed-effect model using restricted maximum likelihood estimation is a full information approach and leads to unbiased model parameter estimates in the presence of MCAR or MAR missingness. Selection between two common covariance structures, Toeplitz and AR(1), will be accomplished using the Akaike Information Criterion (AIC).

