7.2.1 Full Analysis Sample (Intention to Treat)

- All subjects who were randomized
- The ActiGraph monitor was worn for > 4 days of 10 hours of wear time each time point (baseline, discharge, and 6 months).
- This sample will be the primary efficacy sample

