7.4 Missing Data

(ICH E3; 9.7.1, 11.4.2.2. ICH E9;5.3. EMA Guideline on Missing Data in Confirmatory Clinical Trials)

Missing data will be given careful attention in the analysis. In this RCT we have two treatment arms and four fixed times tied to the recovery process for measurements. It is anticipated that drop-outs from the study will be limited because all have elected to undergo knee replacement surgery and would be working toward recovery. However, it is possible that participants may not attend all follow-ups. Drastically fewer participants in the final analysis would affect study sensitivity and excessive missed follow-ups would potentially bias model parameter estimates. Under the assumption of limited data that is missing completely at random (MCAR) or missing at random (MAR), the mixed-effect model using restricted maximum likelihood estimation is a full information approach and leads to unbiased model parameter estimates. Selection between two common covariance structures, Toeplitz and AR(1), will be accomplished using the Akaike Information Criterion (AIC).

In the event that assumptions are not met regarding missing value frequency, MAR, or MCAR and missing values are occurring with higher frequency or are truly missing not at random (MNAR), the analysis may be biased. To test the missingness assumptions, missing data will first be summarized by group, time, each design cell, and each of the three covariates, age, sex and body mass index in an effort to graphically or tabularly detect patterns in the variation of missingness. More formally, missing/nonmissing will be taken as a dichotomous outcome in a logistic regression for continuous covariates and will be compared with between and within factors and sex using chi-square tests. Significant logistic regression that will be identified and reported and whose impact on the analysis will be explained if possible.

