9.1 Primary Efficacy Analysis

The primary endpoint of our study is to examine the efficacy of a Physical Therapistadministered physical activity intervention and standardized outpatient PT to increase MVPA over 6 months after discharge from outpatient PT compared to a control group that received standardized outpatient PT.

The statistical model underlying this analysis is a mixed-effects model to examine the main and interaction effects of *group* (Intervention vs. Control) and *time* (BL, DC, and 6M) on MVPA (minutes/day). We will adjust this model for age, sex, and body mass index.

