10.2 Deaths, Serious Adverse Events and other Significant Adverse Events

We will report on the number of serious adverse events and deaths that are possibly or definitely related to the study.

11 Reporting Conventions

P-values ≥0.01 will be reported to 2 decimal places; p-values less than 0.01 will be reported as "<0.01". The mean, standard deviation, and any other statistics other than quantiles, will be reported to one decimal place greater than the original data. Quantiles, such as median, or minimum and maximum will use the same number of decimal places as the original data. Estimated parameters, not on the same scale as raw observations (e.g. regression coefficients) will be reported to 2 significant figures.

12 Summary of Changes to the Protocol and/or SAP

We have modified the primary and secondary study endpoints from the original study protocol (version v.4 20 August 2018). Namely, the original study protocol listed MVPA taken at baseline, discharge, 6 months and 12 months as our primary study outcome. We have since modified this to MVPA taken at baseline, discharge, and 6 months. As well, the original study protocol listed fidelity, safety, and physical function as secondary outcomes. We have decided to investigate these outcomes in a secondary publication/manuscript separate from the primary paper. We will examine changes in steps/day as a secondary outcome in the primary paper. Lastly, we did list tertiary outcomes including self-efficacy for exercise and fear of movement in the study protocol. We will investigate these in secondary papers, and not as part of the primary paper.

13 Listing of Tables, Listings and Figures

This section is to give precise details for each table, listing or figure to be produced.

Mock Table 1: MVPA at each study time point using the ITT sample

	Baseline	Discharge	6 month	12 month
Control				
Intervention				
Control-				
Intervention				

Mock Table 2: Steps/day at each study time point using the ITT sample

	Baseline	Discharge	6 month	12 month
Control				
Intervention				
Control-				
Intervention				

Mock Table 3: MVPA at each study time point using the per-protocol sample

	Baseline	Discharge	6 month	12 month
Control				
Intervention				
Control-				
Intervention				

Mock Table 4: Steps/day at each study time point using the per-protocol sample

	Baseline	Discharge	6 month	12 month
Control				
Intervention				
Control-				
Intervention

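### SAP section 9 states its null as change in MVPA but does not say which contrast decides it, and its promised 6-month estimates do not use baseline MVPA

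*SAP*

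**What the plan says.** Section 9 of the SAP sets the hypothesis: "The null hypothesis is that there is no difference in change in MVPA in the intervention group compared to the control group". The alternative is worded only as a difference between groups, and the hypothesis is called confirmatory. The same section promises model-based means per visit, then: "We will also calculate difference in means and 95% Confidence Intervals between the intervention and control group at each study time point". On testing it says: "We will also calculate 2-sided p-values to determine statistical significance of differences between groups by time in MVPA".

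Section 9.1, the primary analysis, fits main and interaction effects of group and time over three visits: "BL, DC, and 6M) on MVPA (minutes/day). We will adjust this model for age, sex, and body mass index". Section 9 describes the same model over four visits, adding 12 months. Section 7.3 lists age, sex and BMI as the covariates for all analyses; baseline MVPA is not among them. On covariance: "Selection between two common covariance structures, Toeplitz and AR(1), will be accomplished using the Akaike Information Criterion (AIC".

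The first table shell in section 13 is titled "Mock Table 1: MVPA at each study time point using the ITT sample". It has rows for each arm and for their difference, with one column per visit. None of the four shells has a row for change or for a baseline-adjusted difference. Section 7 gives a sample size of 120 with no SD, effect size, correlation, alpha or power.

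**The concern.** A confirmatory analysis needs one contrast that decides it and an estimate that belongs to that contrast. Here the hypothesis is about change, while the estimates are arm differences at single visits. The wording on p-values fits either the interaction or a set of visit-wise tests. Each test is valid at 5% taken alone, but they can disagree, so the conclusion could depend on which is later read as the result.

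The interaction over three visits is significant whenever the arm difference varies enough between any of them. It does not say where. An effect that appears at discharge and is gone by 6 months would count as success on that test, with nothing to show at 6 months.

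The visit-wise difference at 6 months answers the 6-month question. However, the model leaves the group effect at baseline free. With complete data the 6-month difference is then simply the observed difference, apart from age, sex and BMI, and baseline MVPA, already collected, is not used to sharpen it.

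**Working it through.** **Reproducing the sample size.** N=120 cannot be reproduced, since its inputs are not given. With 60 per arm and two-sided 0.05, the effect detectable with 80% power is (1.960 + 0.842) × √(2/60) = 2.802 × 0.1826 = 0.51 SD. The illustration therefore uses 0.5 SD. This does not show what the sponsor assumed.

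**Assumptions.** 60 per arm, complete data, unit SD at every visit, normal theory, two-sided 0.05. ρ is the correlation between visits after age, sex and BMI, taken as 0.2, 0.3, 0.5 and 0.7. Low values are plausible because protocol section 7 enrols people at any time since surgery. Under compound symmetry (CS) all pairs of visits have correlation ρ. Under AR(1) adjacent visits have ρ, so baseline and 6 months have ρ².

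**Degrees of freedom.** (2−1)(3−1) = 2 in section 9.1; (2−1)(4−1) = 3 for the four-visit model in section 9.

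**Power of the 6-month difference.**
- Unadjusted: SE = √(2/60) = 0.1826; power = Φ(0.5/0.1826 − 1.96) = Φ(0.779) = 78.2% at every ρ.
- Baseline-adjusted: SE = 0.1826 × √(1−r²), where r is the baseline to 6-month correlation. For CS (r = ρ) the SEs are 0.1789, 0.1742, 0.1581 and 0.1304. For AR(1) (r = ρ² = 0.04, 0.09, 0.25, 0.49) they are 0.1824, 0.1818, 0.1768 and 0.1592.

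**Power of the interaction.** Under CS the noncentrality is 2 × 0.5² / [3 × (2/60) × (1−ρ)] = 5/(1−ρ) = 6.25, 7.14, 10.0 and 16.7. It is the same whether the 0.5 SD effect is at discharge only or at both follow-up visits. The test is chi-square on 2 df.

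**Disagreement.** One million simulated sets of arm differences per setting; a trial counts when exactly one of the two tests is significant.

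| ρ | 0.2 | 0.3 | 0.5 | 0.7 |
|---|---|---|---|---|
| 6-month power, unadjusted | 78% | 78% | 78% | 78% |
| 6-month power, adjusted, CS | 80% | 82% | 89% | 97% |
| 6-month power, adjusted, AR(1) | 78% | 79% | 81% | 88% |
| Effect at discharge only: interaction significant, CS | 60.3% | 66.5% | 81.5% | 96.4% |
| Effect at discharge only: 6-month difference significant | 5% | 5% | 5% | 5% |
| Effect at both visits: interaction and 6-month difference disagree, CS | 37% | 34% | 28% | 23% |
| No effect: the same two disagree, CS | 7.4% | 7.7% | 8.3% | 8.8% |

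Under AR(1) the disagreement with an effect at both visits is 39%, 37%, 30% and 23.5%.

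**Chance imbalance.** The baseline arm difference has SE 0.1826 SD, so its 95% limit is 1.96 × 0.1826 = 0.36 SD. The unadjusted 6-month difference carries r times that. Under CS this is 0.07, 0.11, 0.18 and 0.25 SD.

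**The case against.** The strongest reply is that the test is less open than it looks. The null is about change, the model contains the group-by-time interaction, and baseline is a level of time, so the interaction does compare change between arms. SAP section 4.2 sets the scope as change over 6 months, and section 12 defines the primary outcome as MVPA at baseline, discharge and 6 months. A 2-df interaction fits both. On that reading, a significant result from a discharge-only effect is not an error, and the visit-wise differences are descriptive output. This largely stands as a reading of intent. It does not supply a sentence naming the interaction as decisive, and it leaves that test without an effect estimate.

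Second, baseline adjustment is mainly about efficiency, and the gain can be small: under AR(1) with ρ of 0.2 or 0.3 it is one percentage point of power or less. Against the 6-month-minus-baseline contrast it also depends on the SDs. With baseline SD 1 and follow-up SD k, the variance saved is (k²+1−2ρk) − k²(1−ρ²) = (1−ρk)², which is zero at k = 2, ρ = 0.5. This stands.

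Third, the disagreement rates under a true effect partly reflect unequal power. Under CS at ρ = 0.2, about three quarters of the disagreements are trials where only the 6-month difference is significant. At ρ = 0.7, about nine tenths are the reverse. The null figures, 7% to 9%, are free of that.

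Fourth, one sentence naming a contrast of the existing model would close the labelling gap. It would, but the 6-month estimate would still make no efficient use of baseline MVPA.

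**Conclusion.** The point holds in a limited form. The plan leaves its decisive contrast unnamed, its natural test (the interaction) has no matching estimate, and the estimates it does promise forgo baseline adjustment. The change is advisable, though nothing here makes the trial invalid.

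A reader might infer more, and the documents do not support it:
- That no test of change is planned. The interaction is one, and table shells without a row for it do not show that it is absent.
- That the visit-wise differences are biased. Under randomisation they are right on average; the cost is precision and sensitivity to a chance imbalance.
- That baseline adjustment would bring a large gain here. Between 0 and 19 percentage points of power is what the assumed correlations give, and the low end is plausible.

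All sizes rest on assumed SDs, correlations, effect, alpha and equal arms, with complete data. The missing label does not depend on any of them.

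**What to change.** 1. Name one primary contrast in sections 9 and 9.1: the baseline-adjusted group difference in MVPA at 6 months after discharge, two-sided 0.05. Label the interaction and the other visit p-values as supportive.
2. Estimate it from a mixed model of the post-baseline visits, with baseline MVPA and its interaction with visit as covariates, plus age, sex and BMI. Use an unstructured covariance, which for discharge and 6 months has three parameters. Do the same for steps/day with baseline steps.
3. Add the adjusted difference and its 95% CI to the mock tables.

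The cost is wording in SAP sections 7.3, 7.4, 9, 9.1 and 9.2.2, one model statement and one row per table shell. No new data are needed.

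The real downside is timing. SAP section 7.5.4 says interim results went to the principal investigator, and protocol section 10 says the interim would use the final analysis. Changing the primary model now invites the question of why. Record the change and its reason in SAP section 12 before the group labels are opened, and report the SAP's present model alongside as supportive.

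Two neighbouring matters need separate handling: the differing wear requirements for the ITT set in sections 7.2.1 and 9, and the visit windows for baseline wear in section 6.4.

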6.4 Study Assessments

(ICH E3; 9.5.1. ICH E9; 2.2.2)

Visit Description	Patient Eligibility Screen and Enrollment	Randomization		Discharge	Follow-up Period	
Study visit: Study Day (Range of assessment periods)	Visit 1: Day 0 (+/- 14 days)	Visit 2: Day 7 (-2, +8 days)	Treatm ent Period ¹	Visit 3: Day² (-14, +30 days)	Visit 4: 180 Days after Discharge (6 month) (-30, +60 days)	Visit 5: 360 Days after Discharge (12 month) (-30, +60 days)
Informed Consent/HIPAA	х					
Demographics/ Medical History	x					
Accelerometer	Х			Х	Х	Х
Randomization		Х				
Adverse Events			Х	Х	Х	Х
 1 – Study intervention will be delivered when the study participant visit PT. The total number of visits will be based on the number of PT visits during the PT episode of care. The number of visits will be based clinically on physical therapist discretion in accordance with standard physical therapy guidelines. 2 – The study visit day varies depending on the duration of outpatient PT 						

Data collected outside of the time windows listed above will be classified as the intended visit the data was to reflect and noted as being outside the time window. Such data will be included in the primary analyses, however we will also perform a secondary analyses excluding data collected outside the time window.

Study Variable	Description	Endpoints	Interpretation	
Age	Age of study participant in years	Minimum 45 years	N/A	
Gender	Self-reported Sex of study participant	Male/Female	N/A	
BMI	Body Mass Index calculated from weight and height.	Body Mass Index calculated from weight and beight		
Race	Self-reported race	Self-reported race White, Black or African American, Asian, American Indian or Alaskan Native, Hawaiian, more than one race, other		
Hispanic	"Do you consider yourself to be Hispanic or Latino?"	Yes/No	N/A	
Health History Questionnaire	The number of comorbidities from a list of 54 possible conditions	N/A	N/A	
Moderate to Vigorous intensity Physical Activity (MVPA)	MVPA calculated from a monitor (ActiGraph GT3x)	Continuous measure. Minimum value 0 minutes/day	Higher values indicate greater time in MVPA	
Steps/Day	Steps/day calculated from a monitor (ActiGraph GT3x)	Continuous measure. Minimum value 0 steps/day	Higher values indicate greater steps taken/day	
Adverse Event	Defined as any unfavorable or unintended diagnosis, sign, symptom, or disease that is associated with the study and that may or may not be related to the intervention.	Continuous number of adverse events	N/A	

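### Optional improvement: with only Toeplitz and AR(1) allowed, the by-visit 6-month CI and p-value rest on an equal-variance assumption that the documents do not support; an unstructured matrix removes it cheaply

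*SAP*

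**What the plan says.** SAP 7.4 (Missing Data) and SAP 9 (Efficacy Analyses) carry the same rule: "Selection between two common covariance structures, Toeplitz and AR(1), will be accomplished using the Akaike Information Criterion (AIC"). Neither section names a heterogeneous-variance version, an unstructured matrix, a robust standard error or any random effect. The protocol names no covariance structure.

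SAP 9 states the hypothesis in terms of change: "The null hypothesis is that there is no difference in change in MVPA in the intervention group compared to the control group". It also promises by-visit results: "We will also calculate difference in means and 95% Confidence Intervals between the intervention and control group at each study time point", followed by "We will also calculate 2-sided p-values to determine statistical significance of differences between groups by time in MVPA".

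Two models are described. SAP 9 has time as "BL, DC, 6M, and 12M) on MVPA (minutes/day"), while SAP 9.1, the primary efficacy analysis, has "BL, DC, and 6M) on MVPA (minutes/day"). SAP 12 confirms that the primary outcome now runs to 6 months. In SAP 13, "Mock Table 1: MVPA at each study time point using the ITT sample" has columns for all four visits and shows the treatment effect only as a control-minus-intervention row at each visit. The SAP does not say which model fills which column.

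**The concern.** A homogeneous Toeplitz or AR(1) matrix has a single variance, so the standard error of the 6-month difference comes from a variance pooled over visits. If MVPA is more variable at 6 months than on average, the CI is too narrow. If it is less variable, the CI is too wide and power is lost.

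Unequal variance is plausible. MVPA has a floor (SAP 6.4: "Minimum value 0 minutes/day"), and Protocol section 7 admits participants at any time since surgery. Nothing in the documents shows it, however, and nothing shows the opposite.

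Both structures also tie correlation to the number of visits apart. Baseline to discharge is a PT episode of variable length, whereas the later visits are set at 180 and 360 days after discharge (SAP 6.4). Equal correlation at equal visit lag is therefore a second unsupported assumption. It matters in the four-visit model.

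At stake are the interval and p-value for the most visible 6-month entry in Mock Table 1, in a trial that SAP 9 calls confirmatory.

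**Working it through.** **Inputs.** From the documents: the two structures and the AIC rule (SAP 7.4, 9), three or four visits (SAP 9.1, 9), 95% CIs and two-sided p-values (SAP 9), N=120 (SAP 7). Assumed: alpha 0.05 (implied by the 95% CI), all SDs and correlations (after covariate adjustment, the same in both arms), and complete data except in step 5. The plan gives no figure on this point to reproduce.

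**1. Method.** For each assumed true covariance S, find the homogeneous matrix V that minimises the expected -2 log-likelihood, log|V| + trace(V⁻¹S). For a contrast c, ratio = model SE / true SE = √(c'Vc / c'Sc). Then type I error = 2(1 - Φ(1.96 × ratio)). Where a calibrated test has 80% power, actual power = Φ(2.80 - 1.96 × ratio). With complete data the ratio does not depend on arm size.

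**2. By-visit 6-month difference, three visits.** Correlations: BL-DC 0.40, BL-6M 0.35, DC-6M 0.65. The fitted variance is very close to the plain average of the visit variances, so the ratio can be checked by hand. For 1:1.1:1.2 the average is (1 + 1.21 + 1.44)/3 = 1.217, and √(1.217/1.44) = 0.919.

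| SDs BL:DC:6M | Ratio | 1.96 × ratio | Type I error |
|---|---|---|---|
| 1.3:1.15:1 | 1.157 | 2.268 | 2.3% |
| 1:1:1 | 1.000 | 1.960 | 5.0% |
| 1:1.1:1.2 | 0.919 | 1.801 | 7.2% |
| 1:1.25:1.5 | 0.845 | 1.656 | 9.8% |

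In the first row power is Φ(2.80 - 2.268) = Φ(0.532) = 70% instead of 80%. AR(1) and Toeplitz agree to within 0.001 in the ratio, so the AIC step gives no protection.

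**3. Change from baseline to 6 months, three visits (the stated null).** For the four patterns above, Toeplitz gives 5.0-5.2% and AR(1) 3.8-4.6%. Adding 1.5:1.25:1 and 1:1.5:2 widens the overall range to 3.8-5.6%. Toeplitz does well because, with three visits, its lag-2 correlation belongs to the BL-6M pair alone, and in these steady SD patterns the BL and 6M variances together are close to twice the average.

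**4. Change from baseline to 6 months, four visits, equal SDs.** Toeplitz now forces BL-6M and DC-12M to share one correlation. Correlations are listed as BL-DC, BL-6M, BL-12M, DC-6M, DC-12M, 6M-12M.
- Set A (.4, .35, .3, .65, .6, .65): true variance of change 2(1 - 0.35) = 1.30. The fitted Toeplitz has variance 0.995 and lag-2 covariance 0.455, so the model variance is 2(0.995 - 0.455) = 1.08. Ratio √(1.08/1.30) = 0.91; type I error 7.4%.
- Set B (.4, .35, .35, .65, .6, .7): 7.5%.
- Set C (.4, .35, .35, .65, .65, .65): 8.2%.
- Set D (all .6): 5.0%.

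AR(1) would give 4.5-4.8% in sets A to C, but AIC prefers Toeplitz there by 4.3 to 10.2 points. For the by-visit 6-month difference in this model (set A, 12-month SD equal to the 6-month SD), the ratios are 1.122, 0.998, 0.935 and 0.878 for the four SD patterns, which give 2.8%, 5.1%, 6.7% and 8.5%.

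**5. Point estimate.** With complete data the covariance choice does not move it. With visits missing at random, it can. Take SDs 1:1.25:1.5, the step 2 correlations, and logit P(missing at 6 months) = -1.5 + z, where z is the standardised discharge value (about 22% missing). Homogeneous Toeplitz then shifts that arm's 6-month mean by about 0.05 SD; unstructured shifts it by about 0. The shift cancels in the group difference when missingness works the same way in both arms, and does not when it differs by arm.

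**6. Parameters.** Unstructured needs T(T+1)/2: 6 for three visits and 10 for four. Toeplitz needs 3 and 4; AR(1) needs 2.

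**The case against.** **The main test is not at fault.** The only stated null concerns change, and SAP 9.1 makes the three-visit model primary. A reader might infer that the primary test has inflated type I error. The figures do not support that: 3.8-5.6% is near nominal. This objection stands and sets the weight of the point. The step 4 result applies to the four-visit model, which SAP 9.1 does not use.

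**The by-visit p-value is one reading.** The sentence on p-values could mean the group-by-time interaction test. That is fair. The by-visit difference and its 95% CI are promised without ambiguity, so the interval is affected on either reading.

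**The SAP may intend more than it says.** Heterogeneous versions of both structures exist, and a mixed-effects model may include a random slope. Neither is ruled out, but neither is named, and a programmer following the text would probably fit the standard forms.

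**Everything rests on assumed inputs.** This also stands. A reader might infer that the 6-month CI will be too narrow. The documents give no SD, so the direction is unknown, and with equal SDs there is no problem. The mild pattern 1:1.1:1.2 makes the SE only about 8% too small.

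**A two-structure AIC rule is already definite.** It is, and that is a merit. But AIC ranks only the candidates it is given, and both share the same restriction.

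**Conclusion.** The point holds as a low-cost improvement, at COULD level. Calibration of the by-visit 6-month interval depends on equal variance across visits, which the documents neither support nor contradict. Under the assumed SDs and complete data, three-visit type I error runs from 2.3% to 9.8%. The test of change in the primary model is not shown to be wrong. In the four-visit model it can reach 7.4-8.2% under Toeplitz, but only if correlations differ at equal visit lag.

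A reader might also infer that the treatment estimate is biased. With complete data it is not. Under the missing-at-random assumption on which SAP 7.4 relies, the unbiasedness it claims also needs an adequate covariance model. Bias in the group difference further requires missingness that differs by arm, and the documents give no evidence of that.

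**What to change.** In SAP 7.4 and 9, replace the Toeplitz/AR(1) choice with an unstructured within-person covariance, with no added random effects, for both the three-visit and four-visit models. Add a small-sample degrees-of-freedom method such as Kenward-Roger. Use heterogeneous Toeplitz, then heterogeneous AR(1), only if the unstructured model does not converge. State which model fills each column of Mock Table 1.

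The cost is about one sentence in each section and one option in the model code. The statistical price is 3-4 more covariance parameters with three visits (6 against 3 or 2) and 6-8 more with four (10 against 4 or 2), which is small at N=120.
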